9.2.2 INFORMED CONSENT

The Investigator or designee will explain that the patients are under no obligation to enter the trial and that they can withdraw at any time during the trial, without having to give a reason.

The first page of the survey will contain the PIS and consent statements, participants will be asked to sign proof the reading of the PIS.

The return of the completed questionnaire filled in the survey platform will be assessed also as 'implied consent'. No separate documented study consent will be sought. The consent to interview will be also recorded using a tape recorder.

10 STUDY COMMENCEMENT

The study will only commence once evidence of the following approval/essential documents are in place:

1. HRA approval,
2. Final sponsorship and host site confirmation of capacity and capability.

Phase 1 and phase 2 will start in parallel. The recruitment process for **phase 2** will happen in the RFH ITU. The CI and her delegate will approach ITU professionals and ask them to do the survey on a computer or a tablet or a mobile phone. An email will be circulated to the ITU staff containing the survey link.

11 DATA MANAGEMENT AND QUALITY ASSURANCE

Data collection points:

- Retrospective data collection: 1st of July – 30th of October 2020
- Survey: 1st of July – 31st of July 2020
- Interviews: 15 July – 31st of Sept 2020

11.1 CONFIDENTIALITY

All data will be handled in accordance with the Data Protection Act 1998.

The data collection forms will not bear the subject's name or other directly identifiable data. The subject's trial Identification Number (ID) only, will be used for identification. The sponsor Subject ID log RFLRD0002 should be used to cross reference subject's identifiable information.

11.2 DATA COLLECTION TOOL

Data Collection Forms will be designed by the CI and collaborators. All data will be entered legibly in black ink with a ball-point pen. If the Investigator makes an error, it will be crossed through with a single line in such a way to ensure that the original entry can still be read. The correct entry will then be clearly

inserted. The amendment will be initialled and dated by the person making the correction immediately. Overwriting or use of correction fluid will not be permitted.

It is the Investigator's responsibility to ensure the accuracy of all data entered and recorded in the forms. The Staff Delegation of Responsibilities Log RFLRDLOG0004 will identify all trial personnel responsible for data collection, entry, handling and managing the database. The data custodian for this study is [name].

For phase 1, data is to be recorded directly onto the CRF by the CI and the study management team. The data collected is listed in section 9. For phase 2, survey data will be exported in an excel file and kept in a password coded computer. The interview transcriptions will be kept anonymised in word files and saved in a password coded computer for the thematic analysis while the recording destroyed soon after being transcribed.

11.3 INCIDENTAL FINDINGS

Establish the capacity for inadvertent/incidental data that are of potential relevance for participants or their families.

In case of the accidental finding of mental health issue related to managing patients in an unfamiliar environment, the participants will be advised to seek help via their line managers.

11.4 DATA HANDLING AND ANALYSIS

Quality Control should be applied at each stage of data handling to ensure that all data are reliable and have been processed correctly.

Data will be kept in Microsoft office files, the quantitative data in excel files, the qualitative data in word files. After collecting quantitative data in the CRF, data will be exported in the files in an encrypted computer.

11.5 TRANSFERRING/TRANSPORTING DATA

Person-identifiable information will not be stored on any portable device. Identifiable information will not be sent outside the Trust. If needed, data will be transferred electronically in accordance with the UK Data Protection Act 2018 and GDPR.

12 ARCHIVING

During the course of research, all records are the responsibility of the Chief Investigator and must be kept in secure conditions.

The trial essential documents along with the trial database will be archived in accordance with the sponsor SOP0044. The agreed archiving period for this trial will be **5 years**. This will include any study databases.

13.0 ANALYSIS DESIGN

[name] will be responsible with the CI for the data analysis.

13.1 Phase 1 ENDPOINTS

13.1.1 PRIMARY ENDPOINTS

- Proportion of patients who experienced any of the following adverse events possibly correlated with the use of AnMach: soda lime issues, gas flow issues, hypoxia, elevate pressure of ventilation, water need to be cleaned out of tubes, sudden respiratory rate increase, need for manual ventilation (frequency).
- Proportion of ventilation weaning failure while on AnMach (frequency) – This is defined as meeting one of the following criteria:
 - Lack of progress on AnMach – Defined as a failure to reduce ventilatory support for period of > 48 hours
 - Need for ventilation on an ITU grade ventilator – This will be a measured event of the transfer from AnMach to ITU-grade ventilator

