4.0 STUDY FLOW CHART

5.0 INTRODUCTION

5.1 BACKGROUND

The COVID-19 pandemic dramatically increased the demand for the ventilator beds in the United Kingdom (UK), generating, at the same time, Intensive Therapy Unit (ITU) ventilators shortages (Lauer et al., 2020). Anaesthetic machines (AnMach) have been commonly used as a solution to supplement ventilator capacity. The use of AnMach as a long-term ventilator is considered an off-label use but emergency use of these devices is justified when there is no available alternative because the benefits outweigh the risks (Government UK, 2020; Food and Drug Administration Staff 2020). This occurred at the Royal Free Hospital (RFH), London, in April and May 2020.

Modern AnMach are capable of providing mechanical ventilation to patients with respiratory failure, however they neither are ITU grade ventilators nor their use as such has been verified and validated

(GE Healthcare, 2020). Safe and effective use of AnMach as ventilators requires understanding of the differences between AnMach and ITU ventilators and their limitations in mimicking ventilation strategies (APSF/ASA, 2020).

Both machines provide air and oxygen from a wall to patients at desired ventilation settings and oxygen concentration. The AnMach have a rebreathing system where the expired air goes through a filter (soda lime, that has a limited capacity of absorption and needs replacing) that catches the carbon dioxide and the “cleaned” air goes back to the patient. To do this they need high flow volume, more than 50% of the patients’ minute volume (air volume given to patients each minute). The ITU ventilators are non-rebreathing systems so exhaled breath is dispersed to the atmosphere and a new air mix is given to patients at every breath. AnMach are designed to be full time attended because they have limited ability to generate alerts. Also, they may contain residual anaesthetic gas in the system that could interact with other patients’ medication. AnMach need testing every 24hours and need to be set ready to ventilate while ITU ventilators are ready to go as soon as the patient is connected (GE Healthcare, 2020).

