This involves applying the inclusion criteria listed above to patients admitted to 2NA and main recovery between the 1st April 2020 and 1st June 2020. The list of these patients will be generated using the records from the Cerner EPR Computer System where all patient locations within the hospital are updated in a 'live' fashion. This will give us an accurate picture of all the patients admitted to 2NA and main recovery during the above period thus providing a population of patients who were exposed to ventilation by AnMach. In order to identify individuals who were ventilated by AnMach while in this location, we will review the nursing charts and the physiotherapy notes which we anticipate will provide evidence for the method ventilating a particular patient in that location of the hospital

2. Review of raw data:

Following identification of study participants using the inclusion criteria (Section 8.1.1), data from their admission will be reviewed and collected. This will involve manual review of the following:

- Observation charts (when released for review). These provide quantitative data and trends can be identified to provide evidence that ventilatory support was being weaned or escalated:
 - These charts will show hour by hour trends in the level of respiratory support being delivered to the patients, including; the mode of ventilation, the delivered oxygen concentration, the pressure settings of ventilation, position of the patient (i.e. whether prone or not).
 - They also show the physiological status of the patient including their hourly observations and regular blood gas sampling, thus providing evidence about

- whether the patient was deteriorating, improving or remaining static in terms of ventilatory support.
- The chart may also provide qualitative evidence of a patient weaning from ventilation. The back of the chart provides space for the nursing staff to record information regarding the course of the day using 'free-hand'. This will provide evidence of the ventilator being used as well as the clinical direction of the patient i.e. whether weaning or not.
 - Daily review sheets filled in by ICU clinicians and physiotherapists.

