 - These will provide more information about the progress of patients while being ventilated. There may be documentation that mentions difficulties that have arisen when ventilating or weaning ventilation in these patients as well as providing indications as to why patients have been switched to different modes of ventilation or device.
 - Physiotherapists' notes may help us to identify the AnMach patients.

3. Data recording and translation to Outcomes/Endpoints

The data for each patient will be recorded and anonymised in an encrypted Excel spread sheet and will include:

- Age, gender
- Reason for admission
- APACHE II score
- SOFA score
- Date of admission to ICU
- Date of intubation
- Was patient ventilated using AnMach?
- Number of days of ventilatory support before weaning ventilation
- Number of days spent weaning from ventilation to being successfully weaned from ventilator (extubation)
- Was patient transferred from AnMach onto conventional ICU ventilator?
- How many days following ventilation with the AnMach did the transfer happen?
- What was the indication for transferring a patient from an AnMach to the conventional ICU ventilator?
- Did the patient receive a tracheostomy?
- Adverse events possibly correlated with the use of AnMach: soda lime issues, gas flow issues, hypoxia, elevate pressure of ventilation, water need to be cleaned out of tubes, sudden respiratory rate increase, need for manual ventilation
- Organ support - number of days of
 - Use of one or more inotropic drugs or anti arrhythmic

- Renal - a need for renal replacement therapy
- Liver - correction of coagulopathy (plasma use), hypoglycaemia (glucose use), presence of hyperlactataemia (high lactate levels) related to liver failure
- Neuro - delirium
- Date of discharge from ICU or date of death
- Length of ITU stay

The above data will be used to identify quantitative values for the primary and secondary endpoints discussed in section 13.1. This will then be analysed as discussed in Section 13.0

9.1.1b - a prospective data collection

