13.1.2 SECONDARY ENDPOINTS

- Number of patients ventilated with an AnMach in the period of interest (continuous)
- Age (continuous), gender (categorical)

- Reason for admission (categorical)
- APACHE II score (continuous)
- SOFA score (continuous)
- Duration of ventilation - a measurement of the time from the start of ventilation until the first period of mechanical ventilation is complete (continuous)
- Length of ICU stay – A measure of the number of days between admission to ICU and discharge from ICU (continuous)
- Number of days of ventilatory support before weaning ventilation (patients on spontaneous breathing) (continuous)
- Number of days spent weaning from ventilation to being successfully weaned from ventilator (extubation) (continuous)
- Number of days following ventilation with the AnMach after which transfer to an ITU grade ventilator happened (continuous)
- Indication for transferring a patient from an AnMach to the conventional ITU ventilator (categorical)
- Proportion of patients receiving a tracheostomy (frequency)
- Organ support - number of days of (continuous)
 - Use of one or more inotropic drugs or anti arrhythmic
 - Renal - a need for renal replacement therapy
 - Liver - correction of coagulopathy (plasma use), hypoglycaemia (glucose use), presence of hyperlactataemia (high lactate levels) related to liver failure
 - Neuro - delirium
- Length of hospital stay - A measure of the number of days between admission to Hospital and subsequent discharge from hospital (continuous)
- Mortality at 28 days – proportion of patients who died in the study period (frequency)

▪

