13.2 STATISTICAL ANALYSIS PLANS

The retrospective (and prospective, if available) data collection:

This is a cohort study with no sample size calculation. The number of patients managed on AnMach and charts available (identified as AnMach Use) will dictate how many cases we will be able to analyse. The statistical analysis will be descriptive and performed with the Microsoft Office Excel data analysis package in case we will not be able to identify the AnMach charts and we will collect only adverse events data and report them as proportions. The clinical outcomes will be described using absolute and relative frequencies (expressed as a percentage) or position indices (average or median) and relative dispersion indices (standard deviation or interquartile range) suitable for the type of variable analysed. If comparison between AnMach patients and ITU ventilator patients will be possible, mean and standard

23

deviation of clinical outcomes for the two groups will be compared (the plan for this analysis will be explained in case of requesting a protocol amendment).

The Survey:

The questionnaire answers will be inserted in an excel spreadsheet and cleaned. Incomplete, inaccurate and missing data will be detected and discussed during interviews. The results will be used to select participants for the second stage and implement the topic guide for interviewing the volunteers. For this aspect of the study the statistical analysis will be descriptive and performed with the Microsoft Office Excel data analysis package. Data will be reported as proportions.

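### The primary adverse-event proportion has no at-risk window or exposure denominator, and time on the anaesthetic machine is recorded directly only for transferred patients

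*Protocol*

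**What the plan says.** The first primary endpoint in Protocol 13.1.1 is the "Proportion of patients who experienced any of the following adverse events possibly correlated with the use of AnMach". Seven kinds of event follow, among them soda lime problems, water to be cleared from the tubing, hypoxia and the need to ventilate by hand. Section 13.2 says that if charts cannot be labelled by device, "we will collect only adverse events data and report them as proportions". Neither section sets a period in which an event must fall, or a denominator of machine days.

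The background (5.1) describes the absorbent as "soda lime, that has a limited capacity of absorption and needs replacing". Its list of known problems adds that filters become saturated, that water gathers in low parts of the circuit, and that the circuit has to be drained at intervals.

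The data list in 9.1.1a, item 3, contains these items on exposure:

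- "Was patient ventilated using AnMach" (a yes/no item)
- "Date of intubation"
- whether the patient was transferred to an ITU ventilator, why, and "How many days following ventilation with the AnMach did the transfer happen"
- days before weaning, days of weaning to extubation, and the date of ICU discharge or death

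Section 11.2 refers back to section 9 for what is collected. Days to transfer and duration of ventilation are secondary endpoints (13.1.2). Transfer to an ITU ventilator counts as weaning failure in the other primary endpoint (13.1.1).

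**The concern.** Section 7.1 presents Phase 1 as a cohort study of the effect of exposure to AnMach ventilation on adverse events, but the amount of exposure does not enter the endpoint. Half a day and three weeks on the machine carry the same weight, and repeat events in one patient disappear. For event types that build up with use, an ever/never proportion rises with time on the machine even if the daily frequency is constant. A reader of the final percentage could not tell frequent events from long exposure.

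The data list does not allow this to be repaired later. AnMach days are given directly only for transferred patients. For the rest they must be inferred from intubation date and ventilation duration, neither of which is specific to a device. Without event dates, no event can be placed inside or outside AnMach time. An analysis plan written later could not compute a rate from dates that were never abstracted.

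Option II in 9.1.1a, which the protocol thinks more likely, adds a second problem. Events are taken from the charts of everyone admitted to 2NA and main recovery, and nothing ties an event to the time spent there. Events from time on another ventilator may be counted. Days from AnMach start to transfer would also be hard to establish if the device is unknown.

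**Working it through.** The protocol states no event rate, no AnMach duration and no sample size calculation (13.2), so there is no figure to reproduce. The study summary (3.0) gives a maximum of 15 patient datasets. All rates, stays and shares below are assumptions, used to show the mechanism and its possible size.

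**1. Dependence on time.** With a constant rate r per AnMach day, the chance of at least one event in t days is 1 − exp(−r·t).

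| Assumed rate per day | 2 days | 10 days |
|---|---|---|
| 0.05 | 10% | 39% |
| 0.10 | 18% | 63% |
| 0.20 | 33% | 86% |

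**2. Effect on the reported proportion.** Take 15 patients, of whom k have 2 AnMach days and the others 10. The expected proportion is [k·(1 − exp(−2r)) + (15 − k)·(1 − exp(−10r))] / 15. For r = 0.10 and k = 5 this is (5 × 0.181 + 10 × 0.632) / 15 = 0.482. Total AnMach days are 2k + 10(15 − k).

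| k | AnMach days | r = 0.05 | r = 0.10 | r = 0.20 |
|---|---|---|---|---|
| 0 | 150 | 39% | 63% | 86% |
| 3 | 126 | 33% | 54% | 76% |
| 5 | 110 | 29% | 48% | 69% |
| 8 | 86 | 23% | 39% | 58% |

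Within each rate column the rate per day is identical in every row. Only the mix of stays changes.

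**3. Direction.** Some listed events could themselves lead to a transfer. Let q be the share of early transfers triggered by a listed event. A patient moved off at day 2 then scores an event with probability q + (1 − q)(1 − exp(−2r)). For r = 0.05 and q = 0.50 this is 0.50 + 0.50 × 0.095 = 0.548.

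| r | q = 0 | q = 0.25 | q = 0.50 | q = 0.75 | 10-day patient |
|---|---|---|---|---|---|
| 0.05 | 10% | 32% | 55% | 77% | 39% |
| 0.10 | 18% | 39% | 59% | 80% | 63% |
| 0.20 | 33% | 50% | 67% | 83% | 86% |

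Early-transferred patients lie below the 10-day patients in some cells and above them in others (r = 0.05 with q of 0.50 or more; r = 0.10 with q = 0.75). The direction of the distortion is not fixed.

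**The case against.** A reader might infer that patients who fail early and are moved off the machine will look safest. The protocol does not support that. Transfer is scored as failure in the other primary endpoint. Days to transfer and its indication are collected for exactly these patients. Step 3 shows that the ordering can reverse when listed events trigger the transfer. Nor does 13.1.1 say that event counting stops at transfer.

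A reader might also infer that patients who were never transferred have no exposure information. That goes too far. Patients on an ITU ventilator from admission are excluded (8.1.2), so for many of the others intubation date and ventilation duration will approximate AnMach time. The proxy is imperfect, for example when intubation took place before the AnMach was started.

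It would be too strong, too, to say that the result cannot be used. The stated aim (6.1) is to find problems that the guidelines do not describe, and an ever/never count can serve that. The idea that the study may inform practice in a second peak appears in section 18 as a public representative's view. The analysis is descriptive, and no comparison between ventilator groups is planned (13.2.2).

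Three further points have weight. The daily rates are invented. A constant rate fits poorly with events that build up over time, and a pooled rate per 100 days would hide such build-up. With 15 patients, sampling uncertainty is large in any case: the exact 95% interval around 8 of 15 runs from 27% to 79%. These points limit the importance of the concern. They do not supply the missing window, exposure times or event dates, and an unknown direction is a reason to record exposure.

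**Conclusion.** The concern holds in limited form. The first primary endpoint has no at-risk window and no exposure denominator, AnMach days are recorded directly only for transferred patients, and event dates are not listed. The proportion therefore mixes event frequency with length of exposure, and under Option II it may include events from time off the machine.

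The actual size cannot be derived from the protocol. With assumed stays of 2 or 10 days and a constant rate of 0.05 to 0.20 per day, moving eight of 15 patients from the long to the short stay lowers the expected proportion by 16 to 29 percentage points (39% to 23%; 86% to 58%, from unrounded 86.5% and 57.9%). That calculation takes transfers to be unrelated to events; if events prompt transfers, the shift may be smaller or reversed.

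This weakens the interpretation of one descriptive figure and invalidates no stated calculation. It should be corrected before charts are abstracted, because it cannot be recovered from the data set afterwards.

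**What to change.** In 9.1.1a, item 3, add the start and stop date and time of every AnMach episode and the date of each listed event. Where the chart does not show the device, use entry to and exit from 2NA/main recovery in the electronic record, in which "all patient locations within the hospital are updated" live and which the protocol already uses to find patients.

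In 13.1.1, count only events inside that interval. Beside the patient proportion, report events per 100 AnMach days (or location days, labelled as such) and the distribution of exposure days for all patients. The event dates would also let the authors show whether events cluster late in a stay, which a pooled rate hides.

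The cost is a few extra fields, taken from charts and location records already under review, for at most 15 datasets, and a few descriptive lines in the report. The drawback is that under Option II location days only stand in for AnMach exposure, and the report should say so.

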5. Increasing resistance to gas flow due to saturation of filters with water: water vapour is produced by CO₂ absorbers. If the water is not expelled, monitors may indicate easily overlooked flow tracing errors (prolonged expiratory phase, slurring of the expiratory capnography) and increased airway pressure may occur. Periodic drainage of water from the circuit is required which may result in an alternative means of ventilation being used.
6. Collection of water in dependent areas (part of tubes where water sits lower by gravity) of the breathing system: pressure/flow oscillations may be sensed by the ventilator as patient inspiratory effort which in turn will make a total respiratory rate greater than the set one and have a detrimental effect on patient's ventilation.
7. Lack of leak compensation in case of a leak of air flow: this may result in loss of inspiratory pressure and end-expiratory pressure and falling of the bellows (the bag where air flow goes in to be subsequently pushed into patient's lungs) resulting in inadequate ventilation. Several strategies need to be employed including manual ventilation during suctioning of secretions.
8. A 'backup mode' of ventilation is not always present: the lack of the apnea mode (if patients doesn't breathe the system starts ventilating for him) may result in prolonged apnea if patient loses respiratory drive while on spontaneous mode of ventilation.

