7.1 METHODS

This project consists of two parallel phases:

Phase 1, a quantitative, observational, cohort study to detect the effect of exposure to anaesthetic machine ventilation of COVID-19 patients in term of adverse events.

The quantitative phase may be also divided in two parts:

1a, a retrospective data collection of patients admitted to RFH ITU (and possibly the Barnet Hospital ITU) and connected to anaesthetic machines between the 1st April and 1st June 2020, and

1b, a prospective data collection of cases that occur between the 1st June and the 30th October 2020 in order to cover a new period of possible COVID-19 surge.

Phase 2, a survey and an interview stage engaging ITU professionals that managed patients on anaesthetic machines during the COVID-19 surge in an unfamiliar environment (nurses, physiotherapists, and doctors).

Mixed methods were chosen to integrate elements of quantitative and qualitative research in order to achieve a broader understanding of the topic. Also using both methods and integrating results helps determining the interview phase sample and interpreting the findings of the quantitative phase (O'Cathain et al., 2007).

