13.2.2 PRIMARY AND SECONDARY ENDPOINT ANALYSIS

The analysis of Phase 1 of the study will be **descriptive** in nature in case it will be not possible identify patients on AnMach from the charts. There will not be statistical comparison between patients identified as being ventilated by anaesthetic machines and those identified as being ventilated by conventional ITU ventilators. The study will not be sufficiently powered to measure a statistical significance of primary and secondary outcomes between the two cohorts of patients.

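### The primary any-of adverse-event composite mixes expected machine upkeep, signs of lung disease and device faults without an attribution rule, and no single-group proportion can show an effect of exposure

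*Protocol*

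**What the plan says.** Section 13.1.1 of the protocol defines the first primary endpoint as the "Proportion of patients who experienced any of the following adverse events possibly correlated with the use of AnMach". The list is "soda lime issues, gas flow issues, hypoxia, elevate pressure of ventilation, water need to be cleaned out of tubes, sudden respiratory rate increase, need for"; the seventh item, cut short here, is ventilation by hand. One item is enough for a patient to count. No item has a threshold, a severity grade or a rule linking it to the machine, beyond the statement that a correlation is possible.

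Section 5.1 describes several of the same items as part of running the machine:

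- **Soda lime:** "soda lime, that has a limited capacity of absorption and needs replacing".
- **Water:** "Periodic drainage of water from the circuit is required which may result in an alternative means of ventilation being used".
- **Manual ventilation**, under lack of leak compensation: "Several strategies need to be employed including manual ventilation during suctioning of secretions".

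Section 7.1 describes Phase 1 as a "cohort study to detect the effect of exposure to anaesthetic machine ventilation of COVID-19 patients in term of adverse events". On the analysis, Section 13.2.2 says "There will not be statistical comparison between patients identified as being ventilated by anaesthetic machines" and those on conventional ITU ventilators, and adds that power would be insufficient. Section 13.2 makes the analysis descriptive and leaves any comparison to a later amendment. Section 9.1.1a expects Option II, in which the charts do not show which device was used and events are taken from all patients in the two locations.

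**The concern.** Three kinds of event enter one yes/no figure: steps that the protocol expects during normal use, signs that a critically ill COVID-19 patient may show on any ventilator, and faults of the machine. A patient managed as Section 5.1 describes, with no fault, could count the same as a patient harmed by one. The pooled percentage then says little about which hazard matters.

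The second problem is one of purpose. Section 7.1 promises an effect of exposure, and a reader who takes that at face value would credit the whole percentage to the machine. The planned analysis cannot support that reading.

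**Working it through.** **Inputs.** Seven items under an any-of rule (Section 13.1.1); at most 15 patient datasets (Section 3.0); no comparator (Section 13.2.2); no sample size calculation (Section 13.2). The protocol gives no expected rate for any item or for the composite, so there is no figure to reproduce. All rates below are assumptions.

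**Step 1. How items and Background line up.**

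| Item in 13.1.1 | What Section 5.1 says | Possible sources |
|---|---|---|
| Soda lime | limited capacity, has to be replaced | upkeep or fault |
| Water in tubes | drainage is required | upkeep or fault |
| Manual ventilation | a needed strategy during suctioning | upkeep or fault |
| Gas flow | flow settings are a known problem; a 4-hourly increase is advised | fault, possibly upkeep |
| Hypoxia | hypoxic mixture possible at low flows | machine or disease |
| Raised pressure | no relief valve; wet filters | machine or disease |
| Respiratory rate rise | water in the circuit sensed as patient effort | machine or disease |

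Nothing in Section 13.1.1 says which source has to be shown before the item counts.

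**Step 2. Size of the composite.** For independent items the rate is 1 − Π(1 − pᵢ). With an equal rate p it is 1 − (1 − p)⁷:

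- p = 5%: 1 − 0.95⁷ = 30%
- p = 10%: 1 − 0.90⁷ = 52%
- p = 20%: 1 − 0.80⁷ = 79%
- p = 30%: 1 − 0.70⁷ = 92%
- p = 40%: 1 − 0.60⁷ = 97%

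Independence is not needed for a floor, because the composite is never below its most frequent item. If drainage were charted in 95% of patients, the composite would be at least 95% whatever happened to the other six. Positive dependence pulls the figure below the independent value, towards that floor.

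**Step 3. How little a real fault moves it.** Suppose the soda lime, water and manual ventilation entries are all routine, the three signs all come from disease, and gas flow is the only true fault.

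- Upkeep 60% each, signs 50% each: without a fault 1 − 0.4³ × 0.5³ = 99.2%; with a fault in 20% of patients 1 − 0.008 × 0.8 = 99.4%.
- Upkeep 30% each, signs 20% each: without a fault 1 − 0.7³ × 0.8³ = 82.4%; with it 86.0%.
- All items 10%: without a fault 1 − 0.9⁶ = 46.9%; with a fault in 10% of patients 52.2%.

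The last line shows that the pooling matters without saturation too: about 47 of the 52 percentage points would be there with no machine fault.

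**Step 4. What one group can say about an effect.** An exposure effect is the event proportion on the anaesthetic machine minus the proportion the same patients would have had on an ITU ventilator. Only the first term is observed. If 12 of 15 patients (80%) had an event, the second term could be anything from 0% to 100%, so the difference could be anything from +80 to −20 percentage points. Under Option II even the first term is uncertain, because the device behind each chart may be unknown.

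**The case against.** - **The list is deliberate.** Section 5.1 presents drainage and manual ventilation among the commonest issues with these machines, and the aim in Section 6.1 is to identify issues. Counting such burdens is legitimate, and an entry such as a soda lime issue need not mean every planned replacement. This stands: a reader might infer that the endpoint necessarily scores correct use as harm, but the text only leaves that open.
- **The signs are not mere background.** Section 5.1 gives hypoxia, raised pressure and respiratory rate rise each a machine mechanism. This also stands. The defect is the missing rule for choosing between machine and disease, not the inclusion of the signs.
- **Saturation is not certain.** A reader might infer that the composite will sit near 100%. The protocol gives no rates, Section 9.1.1a warns of partial data, and at 5% to 10% per item the figure is only 30% to 52%. Section 5.1 also links some items causally, so independence may overstate the total.
- **Item-level reporting is partly in reach.** Section 9.1.1a collects the seven items, and Section 13.2 speaks of reporting adverse events as proportions. Datix, the indication for transfer and the interviews may help attribution. Even so, the figure that Section 13.1.1 makes primary is the pooled one.
- **Intervals and person-time.** The lack of a stated confidence interval is a matter for an analysis plan and is not held against the protocol. Rates per day on the machine may be impossible under Option II.
- **The analysis already disclaims a comparison.** True, and that is why the wording of Section 7.1 conflicts with it. The comparison under Option I needs a future amendment and is not part of the current plan.

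**Conclusion.** The point holds in this form. The first primary endpoint pools expected upkeep, signs with two possible causes and device faults, with no attribution rule, so its value cannot be read as a measure of machine-related harm. That conclusion rests on the protocol's own text and needs no assumed rate. The size of the composite does depend on assumptions: 30% to 97% for item rates of 5% to 40% under independence, and never below the most frequent item. It may saturate; the documents do not show that it will.

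Separately, the exposure-effect purpose in Section 7.1 contradicts the descriptive, comparison-free analysis in Sections 13.2 and 13.2.2, whatever proportion is observed. Both faults lie in the endpoint and purpose as this protocol fixes them, so they are not details left to a later plan. They should be corrected, and they do not prevent a useful descriptive study.

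**What to change.** 1. In Section 13.1.1, report each of the seven items as its own proportion, and keep the pooled figure at most as a secondary summary.
2. Group the entries as device-specific faults, expected upkeep and physiological signs. Soda lime, water and manual ventilation entries need a short definition that separates a planned step from an unplanned problem with the machine.
3. Count hypoxia, raised pressure or respiratory rate rise as machine-related only where the chart or a Datix report links it to the machine or to a corrective action on it. Report the rest as unattributed. This works under Option II as well, and needs one attribution column in the data list of Section 9.1.1a.
4. Give events per day on the anaesthetic machine only if the charts identify that time (Option I).
5. In Section 7.1, replace the exposure-effect wording with a statement that Phase 1 will describe the frequency of adverse events in patients exposed to anaesthetic machine ventilation.

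The cost is some redrafting and one extra column for at most 15 datasets. The headline percentages will be lower, and attribution will need some judgement.
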